## 9.7.5 Secondary analyses

## Physical and clinical parameters

[figure not shown]
At each timepoint of interest, the continuous endpoints (eg, laboratory results and electrocardiogram results) and the change from baseline in the continuous endpoints will be summarized descriptively. The change from baseline will be derived for each patient by calculating the difference between the entry closest to each timepoint and the baseline information. Two-sided 95% CI will be calculated when relevant.

#### Treatment interruptions and discontinuations

Time to treatment interruption and time to discontinuation will be analyzed using the Kaplan-Meier method and competing risk-based survival analysis if needed. Reasons for treatment interruption and treatment discontinuation will be summarized descriptively.

#### Omaveloxolone drug overdose

Omaveloxolone drug overdose is defined as any dose higher than the daily recommended dose of 150 mg of omaveloxolone. Time to omaveloxolone drug overdose will be analyzed using the Kaplan-Meier method and competing risk-based survival analysis if needed. The daily dose and the reasons for the drug overdose will be summarized descriptively.

## 9.7.7 Analyses of adverse events and serious adverse events

All SAEs and serious adverse drug reactions (SADRs) will be reported to the MAH's safety vendor (Section 11) by the investigator or by the site staff and listed with information on the patients' baseline characteristics. Additionally, SAEs/SADRs with outcome death, and SAEs/SADRs leading to withdrawal

Final protocol version date: 16 December 2024

from the study will be presented in separate listings. An SADR is an SAE for which there is at least a reasonable suspicion of a causal relationship between the SAE and omaveloxolone.

MedDRA coding version 25.0 or later will be used to classify and tabulate the reportable AEs/ADRs. Frequencies (absolute and percentages) across SOCs for individual events within those classes and PT will be provided and calculated with 95% CIs. SAEs/SADRs will be summarized using counts and percentages for the entire study population and subgroups of interest (as applicable).

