#### Data analysis:

The analyses will be descriptive and presented separately for the omaveloxolone-naive cohort and non-naive cohort. Continuous variables will be described with summary statistics such as n, mean, standard deviation, median, first quartile, third quartile, and minimum and maximum values. For each categorical variable, the frequency and percentage will be reported.

Incidence rates will be calculated by dividing the number of new cases of SAEs (all) and all DILI and CHF AEs by the number of patient-years (PYs) at risk, which will be calculated over the follow-up period. In addition, 2-sided 95% confidence intervals (CIs) of incidence rates will be calculated.

There will be no imputation of missing data except for incomplete start dates for the purpose of time-to-event analyses.

A full annual report will be provided for EMA, and interim analyses on AEs of DILI and CHF are to be performed for the FDA biannually.

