## 9.5 Study size

The design of the study is descriptive; therefore, no formal sample size or power calculation is necessary. The sample size is based on both practical and statistical considerations. The safety context of the study requires that the sample size be sufficient to detect a signal, if any.

The study will aim to enroll approximately 300 patients. Tables are shown which assess the precision of different sample sizes based on the occurrence of any SAE and the occurrence of all DILI and CHF AEs.

Table 9-4 presents scenarios in which a certain proportion of patients will experience SAEs after 1, 3, and 5 years of exposure duration. This is based on the results of Study 1402 Part 2, in which 5 patients reported SAEs in 51 omaveloxolone-treated patients studied for 1 year and the Poisson SAE rate estimate per patient year was 0.098 [Lynch 2021a]. In Table 9-4, confidence interval widths and precision were calculated based on Poisson distribution. With sample sizes between 100 and 300 of 1, 3, and 5 years of exposure duration, the precision is reasonably tight.

Table 9-4. Sample size precision table for any SAE

	N	Years	Patient- Years	Expected Number of Events	Lower 95	Upper 95	Cl Width	Precision (Cl Width/2)
Primary (any SAE)	100	1	100	9.804	0.047	0.181	0.135	0.067
	100	3	300	29.412	0.066	0.140	0.075	0.037
	100	5	500	49.020	0.073	0.130	0.057	0.029
	200	1	200	19.608	0.060	0.152	0.093	0.046
	200	3	600	58.824	0.075	0.127	0.052	0.026
	200	5	1000	98.039	0.080	0.119	0.040	0.020
	300	1	300	29.412	0.066	0.140	0.075	0.037
	300	3	900	88.235	0.079	0.121	0.042	0.021
	300	5	1500	147.059	0.083	0.115	0.032	0.016

Abbreviations: CI=confidence interval; SAE=serious adverse event

In Table 9-5, confidence interval (CI) widths and precision were calculated using the exact confidence interval of Poisson distribution. With a sample size of 300, the precision is tight for all outcomes: smaller than 4% for the primary outcome and smaller than 3% for the secondary outcome (and with a sample size of 100, smaller than 7% and 5% respectively). Table 9-5 is designed for the objective of documenting the occurrence of all DILI and CHF AEs. There were no safety events of DILI or CHF reported in Study 1402,

Final protocol version date: 16 December 2024

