but omaveloxolone has been associated with a higher incidence of ALT and AST increase, and with increases in BNP. For that reason, three different hypothetical rates of DILI or CHF AEs of 1%, 2%, and 5% are presented in Table 9-5.

Table 9-5. Sample size precision table for DILI or CHF AEs

	N	Year	Patient- Years	Rate	Expected Number of Events	Lower Upper 95 95	CI W	/idth	Precision (CI Width/2)
	100	1	100	0.01	1	0.000	0.056	0.055	0.028
	100	3	300	0.01	3	0.002	0.029	0.027	0.014
	100	5	500	0.01	5	0.003	0.023	0.020	0.010
	200	1	200	0.01	2	0.001	0.036	0.035	0.017
	200	3	600	0.01	6	0.004	0.022	0.018	0.009
	200	5	1000	0.01	10	0.005	0.018	0.014	0.007
	300	1	300	0.01	3	0.002	0.029	0.027	0.014
	300	3	900	0.01	9	0.005	0.019	0.014	0.007
	300	5	1500	0.01	15	0.006	0.016	0.011	0.005
	100	1	100	0.02	2	0.002	0.072	0.070	0.035
	100	3	300	0.02	6	0.007	0.044	0.036	0.018
	100	5	500	0.02	10	0.010	0.037	0.027	0.014
DILI or	200	1	200	0.02	4	0.005	0.051	0.046	0.023
CHF	200	3	600	0.02	12	0.010	0.035	0.025	0.012
events	200	5	1000	0.02	20	0.012	0.031	0.019	0.009
	300	1	300	0.02	6	0.007	0.044	0.036	0.018
	300	3	900	0.02	18	0.012	0.032	0.020	0.010
	300	5	1500	0.02	30	0.013	0.029	0.015	0.008
	100	1	100	0.05	5	0.016	0.117	0.100	0.050
	100	3	300	0.05	15	0.028	0.082	0.054	0.027
	100	5	500	0.05	25	0.032	0.074	0.041	0.021
	200	1	200	0.05	10	0.024	0.092	0.068	0.034
	200	3	600	0.05	30	0.034	0.071	0.038	0.019
	200	5	1000	0.05	50	0.037	0.066	0.029	0.014
	300	1	300	0.05	15	0.028	0.082	0.054	0.027
	300	3	900	0.05	45	0.036	0.067	0.030	0.015
	300	5	1500	0.05	75	0.039	0.063	0.023	0.012

Abbreviations: AE=adverse event; CHF=congestive heart failure; Cl=confidence interval; DILl=drug-induced liver injury FA is a rare disease; therefore, the decision was made to utilize the existing UNIFAI study and its infrastructure. This strategy provides an efficient way of finding eligible patients. To capture the outcomes of interest, a total follow-up period of five years will be applied for each patient. Because some patients may not complete all five years of follow-up, some assumptions were made regarding attrition. Table 9-6 presents the expected attrition over the course of the study follow-up.

Final protocol version date: 16 December 2024

Table 9-6. Estimated attrition in patients during the follow-up

Exposure Duration (years)	Anticipated # of Patients Completing Follow-up	PYs
1	260	260
3	230	690
5	180	900

Abbreviation: PY=patient-year

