## 9.7.4 Primary analyses

#### All SAEs

An overall summary of TESAEs will be presented, consisting of the number and percentage of patients experiencing the total number of TESAEs. TESAEs will also be summarized by SOC and Preferred Term (PT) (see also Section 9.7.7). TESAEs will be presented overall and by severity and relationship to the omaveloxolone treatment.

Summary listings of TESAEs and SAEs by SOC and PT will be presented with all safety variables.

Where relevant, incidence rate variables will be described as event rates per patient-year (PY) while on treatment. Related two-sided 95% CIs will also be provided.

Final protocol version date: 16 December 2024

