#### DILI and CHF AEs

Incidence rates of all DILI and CHF AEs will be estimated, with two-sided 95% CIs. The diagnostic variables (eg, liver panel, echocardiogram, and/or CHF panel) at the time of each DILI or CHF diagnosis will be summarized descriptively.

SAEs, DILI, and CHF outcomes may also be treated as time-to-event endpoints and analyzed using survival analysis approaches. More details are provided in the SAP.

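### TESAE results by SOC and PT are committed only as crude percentages with 95% CIs; with unequal follow-up these have no time horizon and estimate none of the 1-, 3- or 5-year risks

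*Protocol*

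**What the plan says.** Section 9.7.4 (All SAEs) plans an overall TESAE summary "consisting of the number and percentage of patients experiencing the total number of TESAEs". It then refers the breakdown onward: "TESAEs will also be summarized by SOC and Preferred Term (PT) (see also Section 9.7.7". Section 9.7.7 supplies the content of that breakdown: "Frequencies (absolute and percentages) across SOCs for individual events within those classes and PT will be provided and calculated with 95% CIs". Neither section ties these percentages to a period of follow-up.

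Rates per patient-year appear elsewhere. The abstract (Data analysis) commits to them for the broad categories: "Incidence rates will be calculated by dividing the number of new cases of SAEs (all) and all DILI and CHF AEs by the number". The divisor is time at risk in patient-years, and two-sided 95% CIs are to be given. Section 9.7.4 repeats the commitment for DILI and CHF AEs. For SAEs it adds a conditional sentence: "Where relevant, incidence rate variables will be described as event rates per patient-year (PY) while on treatment". No section commits to a rate by SOC or PT.

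Time-to-event analysis of SAEs, DILI and CHF is optional in section 9.7.4: these outcomes "may also be treated as time-to-event endpoints and analyzed using survival analysis approaches". For the secondary outcomes (interruption, discontinuation, overdose), section 9.7.5 commits to Kaplan-Meier.

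**The concern.** A percentage of all enrolled patients gives a patient seen for one month the same weight as one seen for five years. In this registry, observation time differs for four reasons. Patients enter over about a year. Follow-up ends 60 days after treatment stops. Non-naive patients enter up to 12 months after starting treatment, and their earlier events are not collected. Table 9-6 ("Estimated attrition in patients during the follow-up") expects substantial loss.

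The tables recur in annual EMA reports. A regulator comparing successive reports would see the percentage for a given SOC or PT climb even if the hazard never changed, and could take accumulating follow-up for a signal. A prescriber reading the final percentage could not say which period of treatment it describes. The 95% CI adds apparent precision to a quantity with no defined horizon.

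**Working it through.** **Inputs.** SAE rate 5/51 = 0.098 per patient-year, planned N of about 300, and 260, 230 and 180 patients completing 1, 3 and 5 years (section 9.5, Table 9-6). Enrollment within 12 months (abstract, Assumptions). Cap of 60 months after initiation (section 9.1.2). Annual EMA reports at X + 15 to X + 75 months (section 6).

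**Assumptions added here.** Constant first-event hazard; non-informative dropout, exponential within each interval of Table 9-6; uniform accrual; each data cut three months before its annual report (months 12, 24, 36, 48, 60, 72); every patient followed from initiation, so late non-naive entry is not modelled.

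**1. The plan's own figure.** Table 9-4, 300 patients for 5 years: 1500 × 5/51 = 147.059 events. Exact Poisson limits are χ²(0.025; 2 × 147.059)/(2 × 1500) = 0.083 and χ²(0.975; 2 × 147.059 + 2)/(2 × 1500) = 0.115. Both match the table.

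**2. Attrition.** 1 − 260/300 = 13.3%; 1 − 230/300 = 23.3%; 1 − 180/300 = 40.0%. Dropout hazards per year: −ln(260/300) = 0.143 in year 1; −ln(230/260)/2 = 0.061 in years 1–3; −ln(180/230)/2 = 0.123 in years 3–5.

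**3. Risk at fixed horizons.** 1 − exp(−0.098t) gives 9.3% at 1 year, 25.5% at 3 years and 38.7% at 5 years.

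**4. Share of patients with an observed first event, by length of follow-up.** Each interval contributes S × λ/(λ + h) × [1 − exp(−(λ + h)Δ)]. Here λ is the event hazard, h the dropout hazard, Δ the interval length, and S the share still followed and event-free at its start.

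- Year 1: S = 1, contribution 0.087
- Years 1–3: S = 0.786, contribution 0.132
- Years 3–5: S = 0.571, contribution 0.091

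The running totals are 8.7%, 21.9% and 31.0%.

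**5. Crude percentage at each annual cut.** Average step 4 over entry times spread evenly across the first 12 months, with follow-up capped at 5 years.

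| Data cut (month) | Crude % | Compared with the fixed-horizon risks |
|---|---|---|
| 12 | 4.5 | below all three |
| 24 | 12.4 | above 1-year, below 3- and 5-year |
| 36 | 19.0 | above 1-year, below 3- and 5-year |
| 48 | 24.5 | above 1-year, below 3- and 5-year |
| 60 | 29.0 | above 1- and 3-year, below 5-year |
| 72 (final) | 31.0 | above 1- and 3-year, below 5-year |

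The rise is 31.0/4.5, about 6.8-fold, while the rate per patient-year stays at 0.098. The final figure is 38.7 − 31.0, about 7.8 points before rounding, or 20% in relative terms, below the 5-year risk.

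**6. A rare PT.** At 0.01 per patient-year the risks are 1.0%, 3.0% and 4.9%. The crude figure goes from 0.48% at month 12 to 3.8% at the end.

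**7. Early clustering.** If all events fall in the first 12 weeks with a true risk of 5.0%, the final crude percentage is 4.9%.

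**The case against.** The strongest reply is that the main outcomes are already handled properly. The abstract commits without qualification to rates per patient-year with CIs for all SAEs and for DILI and CHF AEs. The study is descriptive, and an observed proportion of patients with an event is a legitimate count. Survival detail is left to the SAP, which is not at hand. This stands, and it limits the point: the protocol does not lack person-time analysis. What remains is that section 9.7.7 itself fixes a percentage with a CI for SOC and PT, and that time-to-event analysis of the primary outcomes is optional.

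A reader might infer that the percentages understate the 1-, 3- and 5-year risks alike. The arithmetic does not support that. Only a percentage restricted to each horizon would fall short of all three (8.7, 21.9 and 31.0% against 9.3, 25.5 and 38.7%), and the protocol plans no such percentages.

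A reader might also take the section 9.5 phrase "a certain proportion of patients will experience SAEs after 1, 3, and 5 years of exposure duration" as a formal target that the analysis then misses. It is a loose introduction to Table 9-4, whose figures are Poisson rates per patient-year. The CI is therefore not wrong for a stated target; the percentage has no stated horizon at all.

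Comparability of the cohorts is largely addressed, because section 9.7 presents them separately. Delayed-entry estimation in the non-naive cohort also has real limits. Events before enrollment are not collected, and patients must be on treatment to enter, so early risk sets would be thin and selected.

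**Conclusion.** The point holds within a limited scope: the SOC/PT tables, and the absence of a commitment to time-specific risks for the primary outcomes. Under the assumptions stated, the crude percentage grows about 6.8-fold between the first and last annual cuts through accumulating follow-up alone. It ends 20% below the 5-year risk and well above the 1- and 3-year risks.

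The size depends on a constant hazard and non-informative dropout. With early clustering the bias is negligible. If dropout follows SAEs, the size changes in a way the protocol does not allow to be quantified. Since long-term safety is a primary objective, early clustering should not be presumed. This is a worthwhile and cheap improvement; it does not undermine the planned overall rates.

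**What to change.** In sections 9.7.4 and 9.7.7, report SOC and PT results by cohort as counts with events per patient-year and exact Poisson 95% CIs. Keep crude percentages as descriptive figures, with the follow-up time stated beside them.

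In section 9.7.4, replace the optional wording on time-to-event analysis with a commitment to the cumulative incidence of first TESAE, first DILI AE and first CHF AE at 12, 36 and 60 months with 95% CIs, treating death as a competing event, for the naive cohort. For the non-naive cohort, give rates per patient-year from enrollment, and label any delayed-entry cumulative incidence as supportive only.

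The cost is protocol, SAP and table-shell wording and somewhat more programming per report. No additional data are needed.

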## 9.7.8 Subgroup analyses

There are no other defined subgroup analyses. However, subgroup analyses may be conducted if sample size allows.

## 9.7.9 Handling of missing data

There will be no imputation of missing data in this study except for incomplete start dates for the purpose of time-to-event analyses; analyses will be conducted for outcomes where data are available. All efforts will be made to collect data as completely as possible. However, the count and percentages of patients with missing values will be reported for both continuous and categorical variables. Further details on the handling of missing data, eg, partially missing dates, will be described in the SAP.

#### 9.7.9.1 Statistical software

The analyses will be performed using the statistical software SAS version 9.4 or higher.

## 9.8 Quality control

The procedures to ensure data quality and integrity in the EDC, including the accuracy and legibility of the data collected and original documents, extent of source data verification and validation of endpoints, storage of records, and archiving of the statistical programming performed to generate the results, are summarized below and will be described in detail in the monitoring plan, Data Validation Manual, and the SAP. Each document will be a standalone document.

Systems with procedures will be implemented to ensure the quality of every aspect of the study.

The development of the protocol and SAP will follow relevant standard operating procedures (SOPs), which include detailed rounds of review. Quality control of the statistical programming will also follow the relevant SOPs.

The EDC system (Section 14) meets approved, established standards for the security of health information, is validated, and is compliant with 21 Code of Federal Regulations (CFR) Part 11. To ensure that patient data (as well as other confidential data) remain secure and intact, the providing vendor will follow SOPs and quality control processes that address patient data security. The EDC system has built-in edit checks and validations and supports electronically generated and manual queries.

Confidentiality of data shall be observed by all parties involved at all times throughout the clinical study. All data shall be secured against unauthorized access. Sites will maintain patient privacy in accordance with local and national regulations and institutional requirements.

Final protocol version date: 16 December 2024

A unique pseudonym for each patient is created based on fixed data (site number and order of enrollment/consent). The key for the re-identification is held securely at the study site where the patient is registered with this study and can be used for re-identification if in the patient's interest / in case of emergency.

## 9.9 Limitations of the research methods

This study aims to investigate the long-term safety of omaveloxolone in patients treated for FA in a real-world setting. This study's limitations are inherent to non-interventional study design and rare disease studies. Potential limitations and proposed strategies to address them are outlined in the sections that follow.

## 9.9.1 Sample size

Because of the rarity of FA, the precision estimation for this study is limited. To achieve a large enough sample size and to provide clinically meaningful data, the target sample size was calculated using both practical and statistical considerations. Although several factors may affect patient recruitment, notably omaveloxolone market launch and uptake in different countries, continuous monitoring of patient recruitment at the site and country levels will allow the rapid deployment of mitigation strategies in response to any challenges. Such plans will be discussed by the MAH and the regulatory authorities. By using the UNIFAI study to contact investigators and enroll patients, we expect to optimize patient recruitment.

## 9.9.2 Observational study design limitations

Due to the observational nature of this study and the inherent characteristics of such a design, this study may be subject to bias, including selection bias, variability in local treatment practices, guidelines, and data quality across sites.

## 9.9.2.1 Study biases

Selection bias due to non-consent will be mitigated by providing clear information to patients and legal representatives regarding the importance of the study and the absence of burden for them. The extent of the selection bias will be monitored via maintenance of an enrollment log at the site, which will anonymously list all eligible patients, consenting status, and characteristics, and inform the implementation of mitigation strategies. Finally, eligible patients will be included in this study on a consecutively enrolled basis to ensure that they were not selected by the investigator in any way that might influence the nature of the study.

The data provided by the non-naive cohort may be impacted by immortal time bias because patients who initiate omaveloxolone treatment and discontinue due to an SAE or CHF/DILI AE will not have the opportunity to enroll and thus will fail to have their events recorded. Baseline data for this cohort will be collected retrospectively for the period just prior to the initiation date of omaveloxolone treatment and will be subject to recall bias to a greater extent than the omaveloxolone-naive cohort. Data will not be collected between the initiation date of omaveloxolone treatment and the date of enrollment for this cohort, so patients will be missing data varying from Month 1 to Month 6 but, per inclusion criteria, will begin providing prospective data no later than the Year 1 visit. However, even during the prospective data

Final protocol version date: 16 December 2024

collection, where data collection methods are identical between the 2 cohorts, the non-naive cohort may differ from the omaveloxolone-naive cohort in their experience of longer-term safety due to this bias. The mitigation strategy for this potential bias is to perform the analyses separately for the omaveloxolone-naive cohort and non-naive cohort. A sensitivity analysis using survival approaches may also be used to account for immortal time bias in non-naive users.

Most (but not all) FA patients receiving omaveloxolone treatment will also receive care at UNIFAI centers. This study will not be able to observe outcomes in patients who do not receive care at UNIFAI study centers. Some countries in the European Union are participating in the early access program. This may result in reduced recruitment of patients with severe cases of FA.

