### 9.1.2 Study duration and follow-up

This study begins after product availability in a country that has approval for omaveloxolone, and when the first participating site begins enrollment, following approval of the protocol by the relevant ethics committee (EC) or institutional review board (IRB). The study start date is December 2024. Each patient's participation will last no longer than 60 months after omaveloxolone initiation, although treatment is expected to continue past this timepoint.

Participation of each patient will begin at the date of informed consent/assent. The index date will be the date at which prospective data collection begins. For the omaveloxolone-naive cohort, this will be the date of initiation of omaveloxolone treatment. For the non-naive cohort, this will be the date of enrollment. After signing informed consent/assent, the patient will be followed for 60 months following date of initiation of omaveloxolone treatment or for 60 days after discontinuation of omaveloxolone treatment or discontinuation from the study. Discontinuation is defined as an interruption in omaveloxolone treatment in which the patient does not reinitiate omaveloxolone treatment within 60 days of the date of the last administration. The date of treatment discontinuation will be defined as the date of the last administration of omaveloxolone. Patients will have completed the study when they complete 60 months of treatment, discontinue treatment and complete the 60-day safety follow-up, withdraw consent, or death. More details on the study time periods are provided in Section 9.2. A study design schematic is presented in Figure 1.

Final protocol version date: 16 December 2024
Figure 1. Study design schematic

Each patient will be asked to provide informed consent/assent for participation in this study and for marketing authorization holder (MAH) access to relevant medical history data. Once informed consent/assent is signed, the patient will receive their study identification (ID) and move to baseline data collection, following which they will be considered enrolled in the study. The initiation date of omaveloxolone treatment will set the study visit cadence, with each visit scheduled based on time passed from this date.

- For the omaveloxolone-naive cohort, baseline data collection will begin following informed
  consent/assent. If omaveloxolone treatment is not initiated at the time of enrollment and

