#### Inclusion criteria

- Patients aged 16 years and older at initiation of omaveloxolone treatment
- Documented diagnosis of FA, including confirmation via genetic testing
- For the omaveloxolone-naive cohort
  - omaveloxolone naive
  - initiating omaveloxolone treatment as per an approved label concurrent with enrolling in this study
- For the non-naive cohort
  - initiated omaveloxolone treatment as per an approved label less than 12 months prior to enrollment in this study
  - o prior to enrollment, maintained omaveloxolone treatment with no discontinuation of more than 60 days
  - o actively on treatment at the time of enrollment in this study
  - treating physician is the study site principal investigator or sub-investigator
  - study site confirms ability to provide required baseline data through medical record review,
     UNIFAI database, or other site-collected data
- Enrolled in the UNIFAI study prior to initiation of omaveloxolone treatment
- Willing and able to comply with visits as per the relevant approved label, and other study procedures
- Evidence of a personally signed and dated informed consent document (and assent form, if necessary) indicating that the patient (or a legally authorized representative) has been informed of all pertinent aspects of participation in the study prior to data collection for this study

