#### 9.3 Variables

Most variables of interest for this study are being collected as part of the UNIFAI study and will be extracted from the UNIFAI data platform. Information collected as part of this observational study may lead to the need for additional follow-up, management, and treatment of patients, based on the judgment of the investigator. If the investigator is not the treating physician, communication of such judgment by the investigator to the treating physician is generally recommended.

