Descriptions of and incidence data for DILI and CHF events will be collected via the AE/SAE data collection forms. Incidence will be presented for all events of DILI and CHF that occurred from the initiation date of omaveloxolone treatment for the omaveloxolone-naive cohort (with onset date on or after the first treatment of omaveloxolone) or from enrollment date for the non-naive cohort until study completion.

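### Section 9.9.2.1 calls depletion of susceptible patients immortal time bias, and the optional survival analysis as worded does not show how much of a cohort difference comes from that selection

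*Protocol*

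**What the plan says.** Section 9.9.2.1 says that the non-naive data "may be impacted by immortal time bias because patients who initiate omaveloxolone treatment and discontinue due to an SAE or CHF/DILI AE" cannot enroll, so their events go unrecorded. It adds that this cohort may therefore differ in longer-term safety. The main remedy is stated plainly: "The mitigation strategy for this potential bias is to perform the analyses separately for the omaveloxolone-naive cohort and non-naive cohort". The survival analysis is an optional addition: "A sensitivity analysis using survival approaches may also be used to account for immortal time bias in non-naive users". No time scale or entry rule is named, and Section 9.7.4 leaves time-to-event detail to the SAP.

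The surrounding rules are these:

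- **Entry (Section 9.2.2.2).** Non-naive patients started treatment less than 12 months before enrollment, had no gap of more than 60 days, and are on the drug at enrollment.
- **Index date (Section 9.1.2).** "For the non-naive cohort, this will be the date of enrollment".
- **Events counted (Section 9.3.1.1).** From initiation in the naive cohort, "or from enrollment date for the non-naive cohort until study completion".
- **Pre-enrollment data (Sections 9.1.2 and 9.7).** Events between initiation and enrollment are not collected and enter no analysis.
- **Denominator.** The Abstract takes patient-years over the follow-up period. Section 9.1.2 describes that period as 60 months from initiation, and Section 9.7.4 uses patient-years on treatment.

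**The concern.** Immortal time bias arises when event-free time that a patient had to survive is counted in a denominator. Section 9.9.2.1 describes patients missing from the cohort altogether. The two problems need different remedies: the first is cured by moving the start of the clock, while the second needs information on patients who did not survive to entry.

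The label therefore points the sensitivity analysis at the wrong target. If it is run on post-enrollment time, it will agree with the main rate and may be read as evidence that the bias is small.

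The hidden window matters. Section 7.2.1 reports that most heart failure events with a structural analog, in a different population, came in the first four weeks. It also says that the excess of several adverse events in the pivotal trial was generally limited to the first 12 weeks. DILI and CHF incidence is a primary outcome. No DILI or CHF has been reported with omaveloxolone in FA, so an early excess is a possibility to be sized and not a known effect.

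**Working it through.** **Plan's own figure.** The sentence at issue carries no number. As a check on the plan's rate method, Table 9-4 for 300 patients over 5 years gives 5/51 × 1,500 = 147.06 events. The exact Poisson limits are 0.083 and 0.115, as printed.

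**Step 1: does the label fit?** If patient-years start at the non-naive index date (enrollment), numerator and denominator start together and no immortal time is counted. If they start at initiation, a 60-month completer enrolled at month e has the rate multiplied by (60 − e)/60:

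| e (months) | factor | 0.098 per PY becomes |
|---|---|---|
| 1 | 0.983 | 0.096 |
| 6 | 0.900 | 0.088 |
| 12 (limit) | 0.800 | 0.078 |

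The index date favors the first reading, but the denominator wording does not exclude the second.

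**Step 2: how large could depletion be?** The following are assumptions; the protocol gives none of them. A share q of patients has hazard hs per year and the rest h0. Enrollment delay is uniform over 0 to 1 year. Follow-up ends 5 years after initiation. The first event ends treatment, and an event before enrollment excludes the patient.

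Per initiator with hazard h:

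- Naive events: N = 1 − exp(−5h); patient-years N/h.
- Non-naive events: M = (1 − exp(−h))/h − exp(−5h); patient-years M/h.

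For q = 5%, hs = 3, h0 = 0.01:

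- Naive: events 0.05 × 1.0000 + 0.95 × 0.04877 = 0.0963; PY 0.05 × 0.3333 + 0.95 × 4.877 = 4.650; rate 0.0207.
- Non-naive: events 0.05 × 0.3167 + 0.95 × 0.04379 = 0.0574; PY 0.05 × 0.1056 + 0.95 × 4.379 = 4.165; rate 0.0138, which is 33% lower.

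| Scenario | Naive rate | Non-naive rate | Difference |
|---|---|---|---|
| Constant 0.02 | 0.0200 | 0.0200 | none |
| 5% at 1/PY, rest 0.01 | 0.0205 | 0.0174 | −15% |
| 5% at 3/PY, rest 0.01 | 0.0207 | 0.0138 | −33% |
| 8.8% at 12/PY, rest 0.01 | 0.0297 | 0.0118 | −60% |

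A simulation of 2 million initiators gave 15%, 34% and 61% for the last three rows.

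**Step 3: what can a survival analysis change?** For the 5% at 3/PY case:

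- *Events per PY.* Delayed entry uses the same post-enrollment events and time, so the rate stays at 0.0138.
- *Five-year cumulative incidence.* The true value is 9.6%. Timed from initiation without delayed entry it is 0.0574/0.9611 = 6.0%, where 0.9611 is the share who reach enrollment. With delayed entry the simulation gives 9.6%.
- *Years 1 to 5.* The hazard is 0.0107 in both cohorts, so after the entry window they agree.
- *No enrollment before month 6.* Delayed entry gives 1 − 0.9037/0.9564 = 5.5%, the risk conditional on reaching month 6. Earlier risk is not recovered.
- *Precision.* With an assumed 150 non-naive patients, the simulated delayed-entry estimate has a standard deviation of 5.9 percentage points (2.5th to 97.5th percentile about 3% to 22%).

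**The case against.** The strongest reply is that the substance is already disclosed. Section 9.9.2.1 says who is missing, why, and that longer-term results may differ. Its main remedy is separate reporting, repeated in the Abstract and Section 9.7, and the naive cohort, followed from initiation, is reported in its own right. The survival analysis is optional, and its method belongs in the SAP. All of that stands, and no missing method detail is held against the protocol. What remains is that the sentence names the wrong target, and that two separate rates do not show how much of their gap is selection.

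The scenarios can also be faulted, fairly. Shares, hazards and entry pattern are invented, and every event is taken to end treatment. The entry rule bars only patients off the drug or with a gap of more than 60 days, so a patient who had an event and continued, or restarted in time, can still enroll. Depletion is therefore overstated, particularly for SAEs.

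A reader might go further and infer that no survival analysis could change the result. The documents do not support that: they fix no time scale, and delayed entry on time since initiation moves cumulative incidence from 6.0% to 9.6% above. Nor do they support a flat statement that no immortal time is counted, given the denominator wording.

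A reader might also dispute the statement "where data collection methods are identical between the 2 cohorts", because only for the non-naive cohort is it required that the "treating physician is the study site principal investigator or sub-investigator". That is an eligibility condition and not a collection method. The visit schedule and the rules for recording and reporting events are common to both cohorts during prospective follow-up, and Section 9.3's advice on contact with the treating physician does not distinguish cohorts.

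**Conclusion.** The point holds in a limited form. The bias described is left truncation with depletion of susceptibles, and the label should be corrected. Separate analysis is a sound main mitigation but does not isolate the selection effect. The optional survival analysis leaves the planned events-per-PY rate unchanged. It alters cumulative incidence only on time since initiation with delayed entry, and then only if enrollments are spread over the early months and entry is independent of risk.

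The size is not known from the documents: none under a constant hazard, and about 15% to 60% lower non-naive rates in the early-susceptible scenarios, which lean toward overstatement. Separately, the start of non-naive patient-years is worded loosely enough to dilute a completer's rate by 1.7% (entry at month 1) up to nearly 20% (entry close to month 12) if read from initiation. This is an inexpensive improvement to make and does not invalidate the primary analysis.

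**What to change.** 1. In Section 9.9.2.1, replace the term immortal time bias with left truncation (depletion of susceptibles).
2. State once, in the rate definition, that non-naive patient-years start at enrollment, and align the Abstract, Section 9.1.2 and Section 9.7.4 with it.
3. Define the sensitivity analysis as time since initiation with delayed entry at enrollment. Add a landmark analysis: apply the non-naive rule (on treatment, no gap of more than 60 days) to the naive cohort at the observed non-naive entry times, and count events and time from there. Report SAE, DILI and CHF results for the full naive, landmark naive and non-naive groups side by side. Full against landmark naive sizes what the entry rule hides; landmark naive against non-naive is the like-for-like comparison.
4. State that risk before the earliest non-naive enrollment can come only from the naive cohort.

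The cost is protocol and SAP text and one re-analysis of data already being collected. The drawback is small landmark groups and imprecise estimates, especially for DILI and CHF and in the early reports.
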